CPK	Creatine Phosphokinase
CR	Complete Response
CRF	Case Report Form
CTCAE	Common Terminology Criteria for Adverse Events
CTFI	Chemotherapy Free Interval
DB	Database
DCR	Disease Control Rate
DR	Duration of Response
DNA	Deoxyribonucleic Acid
ECG	Electrocardiogram
ECHO	Echocardiogram
ECOG	Eastern Cooperative Oncology Group
EFTs	Ewing's Family of Tumors
ER-/+	Estrogen Receptor -/+
FD	Flat Dose
G-CSF	Granulocyte-Colony Stimulating Factor
GCTs	Germ Cell Tumors
GGT	Gamma-glutamyltransferase
H0	Null Hypothesis
H1	Alternative Hypothesis
hCG	Human Chorionic Gonadotropin
HER-2	Human Epidermal Growth Factor receptor 2

H&N	Head and Neck Carcinoma
IA	Investigator's Assessment
ICH	International Conference on Harmonization
IB	Investigator's Brochure
IRC	Independent Review Committee
i.v.	Intravenous(ly)
K	Potassium
LDH	Lactate Dehydrogenase
LVEF	Left Ventricular Ejection Fraction
MBC	Metastatic Breast Carcinoma
MedDRA	Medical Dictionary for Regulatory Activities
MUGA	Multiple-gated Acquisition Scan
NA	Sodium / Not applicable
NCI	National Cancer Institute
NCI-CTC	National Cancer Institute-Common Toxicity Criteria
NCI-CTCAE	National Cancer Institute-Common Terminology Criteria for Adverse Events
NE	Not Evaluable
NETs	Neuroendocrine Tumors
NOS	Not Otherwise Specified
ORR	Overall Response Rate
OS	Overall Survival
OSI	Office of Scientific Investigations
PD	Progressive Disease
PCI	Prophylactic Cranial Irradiation
PFS	Progression-free Survival
PGx	Pharmacogenomics
PK/PD	Pharmacokinetics/Pharmacodynamics
PR	Partial Response
PR-/+	Progesterone Receptor -/+
PS	Performance Status
PT	Prothrombin Time/Preferred Term
PTT	Partial Thromboplastin Time
q3wk	Every Three Weeks
R	Resistant
RBC	Red blood cell
RD	Recommended Dose
RR	Refractory

RECIST	Response Evaluation Criteria In Solid Tumors
S	Sensitive
SAE(s)	Serious Adverse Event(s)
SCLC	Small Cell Lung Cancer
SD	Stable Disease
SOC	System Organ Class
Std.	Standard deviation
TEAE	Treatment Emergent Adverse Event
TTP	Time to Progression
ULN	Upper Limit of Normal
UK	Unknown
vs.	Versus
VS	Very Sensitive
WBC	White Blood Cells
WHO	World Health Organization
Wk(s)	Week(s)
y	Year

1 STUDY RATIONALE

- The management of advanced small cell lung cancer (SCLC), head and neck (H&N) cancer, neuroendocrine tumors (NETs), biliary tract carcinoma, endometrial carcinoma, BRCA1/2-associated metastatic breast cancer, carcinoma of unknown primary site, germ cell tumors (GCTs) and Ewing family of tumors (EFTs) represents an unmet medical need. Cytotoxic chemotherapy remains a crucial component of their therapeutic armamentarium but there is a need to develop new anticancer agents that broaden the clinical benefit.
- PM01183 is a new chemical entity that induces double-strand DNA breaks through binding to the DNA minor groove. Results of the COMPARE analysis revealed that it is unlikely that this drug shares a similar mechanism of action with any of the other 98 standard cytotoxic agents compared.
- PM01183 has shown antitumor activity in most of the tumor types selected in this clinical study. In the combination trial of PM01183 at 4.0 mg flat dose (FD) with 50 mg/m² of doxorubicin every three weeks (q3wk) (PM1183-A-003-10), five of 12 evaluable patients with SCLC achieved partial response (42.0%), with a median time-to-progression (TTP) of 2.0 months. In endometrial carcinoma, two of three patients treated with the combination PM01183 plus doxorubicin at the aforementioned dose and schedule had a complete response and a partial response, respectively. The third patient had disease stabilization longer than 4 months. The median TTP was 10.1 months. Also with this combination, a patient with NET had a partial response with a TTP of 4.5 months. In a phase II clinical trial of PM01183 as single agent in MBC, one of 54 patients with germline BRCA 1/2 mutation had a complete response (2%) and 21 patients had partial response (39%). Twenty-three additional patients had disease stabilization (43%). One patient with H&N carcinoma treated with PM01183 as single agent at 2.6 mg/m² q3wk achieved a disease stabilization of 4 months duration. Finally, one patient with a carcinoma of unknown primary site treated with PM01183 as single agent at 7 mg FD q3wk had disease stabilization for 2.6 months.
- The inclusion of patients with EFTs is mainly based on the similar mechanism of action of PM01183 and its related compound trabectedin. In sarcomas associated with translocations, such as myxoid liposarcoma, in which the translocation produces a fusion protein (FUS-CHOP) that acts as a deregulated transcription factor, trabectedin has been shown to interfere with the binding of this protein to specific DNA promoters, and hence with the synthesis of downstream proteins. Based on the structural and functional similarities of these fusion proteins, trabectedin could induce on other translocation-related sarcomas similar effects to those described in myxoid liposarcoma. In fact, trabectedin has shown efficacy in advanced pretreated patients with Ewing's sarcoma: three partial responses and seven disease stabilizations in 20 patients, with a 25% 6-month progression-free survival (PFS) rate. Since PM01183 has a favorable pharmacokinetic (PK) profile compared to trabectedin, as shown by a tolerated dose four times higher and an exposure 15.3 times higher than that of trabectedin at the RD, it has been postulated that its effect on rapidly growing tumors such as EFTs would be superior. In addition, an improved therapeutic index of PM01183 relative to trabectedin, as well as suppression of the EFTs fusion protein EWS/FLI1 activity by PM01183 at clinically achievable concentrations, have been reported.

- The finding of PM01183 activity in aggressive tumors with high proliferation index, such as BRCA germline mutation-positive breast carcinomas, neuroendocrine tumors and SCLC, led to the inclusion of GCTs and biliary tract carcinoma in this study.
- In conclusion, this clinical trial has been designed to establish or confirm the proof of concept of PM01183 anticancer activity in several difficult-to-treat tumors for potential further development.

2 STUDY DESIGN

Multicenter, open-label, exploratory, phase II clinical trial to evaluate the efficacy and safety of PM01183 in previously treated patients with the following advanced solid tumors: SCLC, H&N, NETs, biliary tract carcinoma, endometrial carcinoma, BRCA 1/2-associated MBC, carcinoma of unknown primary site, GCTs, and EFTs.

Patients with each of the aforementioned tumors will be enrolled in nine cohorts. Up to 25 evaluable patients are planned to be enrolled in each cohort (50 in the endometrial carcinoma and 100 in the SCLC cohort). To consider that PM01183 has antitumor activity in any of the tumor types analyzed, at least two confirmed responses [complete (CR) or partial response (PR)] per RECIST v.1.1 out of the 25 patients of each cohort are expected.

- If no confirmed responses are observed in the first 15 evaluable patients of each cohort, the recruitment of the corresponding cohort will be stopped.
- If one confirmed response is observed in the first 15 evaluable patients of each cohort, the recruitment of this cohort will continue to up to 25 evaluable patients.
 - In the cohort of endometrial carcinoma, if ≥ 2 confirmed responses occur in the first 25 evaluable patients, the sample size will be doubled to 50 evaluable patients.
 - In the cohort of SCLC, if ≥ 2 confirmed responses occur in the first 25 evaluable patients, the sample size will be increased to 100 evaluable patients.
- If two confirmed responses are observed in the first 15 evaluable patients of each cohort, the recruitment of the corresponding cohort can be stopped.

Only in the SCLC cohort, an IRC will be performed on all images collected and will provide a radiographic response at each time point termed. These data and the clinical database information will be used to derive the independent review efficacy information following the RECIST v.1.1. Operational details for the IRC and the algorithm and its validation by an expert panel is described in detail in the IRC charter.

In addition, for safety reasons:

- If two patients have a treatment-related death in a cohort, the recruitment of the corresponding cohort will be stopped.
- If six patients have treatment-related deaths in the whole population, the study will be stopped.

Finally,

- A determined cohort can be early closed by the Sponsor in case of a low recruitment rate.

- Once the target of patients included in each cohort is reached, recruitment in this cohort will be kept “on hold” during the period of patients’ data analysis to assess their evaluability and the response rate. After this period, if the number of evaluable patients does not reach the planned target, recruitment will be re-opened and non-evaluable patients will be replaced.

Patients will receive the study treatment as long as it is considered to be in their best interest. Specifically, treatment will continue until disease progression, unacceptable toxicity, treatment delay > three weeks from the treatment due date (except in case of clear clinical benefit, upon Sponsors’ approval), requirement of > two dose reductions, intercurrent illness of sufficient magnitude to preclude safe continuation of the study, a major protocol deviation that may affect the risk/benefit ratio for the participating patient, investigator’s decision, non-compliance with study requirements and/or patient’s refusal.

All adverse events (AEs) will be graded according to the National Cancer Institute Common Terminology Criteria for Adverse Events (NCI-CTCAE) v.4.

Treatment delays, dose reduction requirements and reason for treatment discontinuation will be monitored throughout the study. The safety profile of patients will be monitored throughout the treatment and up to 30 days (± 7 days) after the last treatment infusion (end of treatment, EOT), until the patient starts a new antitumor therapy or until the date of death, whichever occurs first. Any treatment-related AEs will be followed until recovery to at least grade 1 or stabilization of symptoms or until the start of a new antitumor therapy, whichever occurs first.

Patients will be evaluated at scheduled visits on three study periods: Pre-treatment, Treatment and Follow-up. This clinical trial will finish (clinical cut-off for each cohort except SCLC cohort) when all evaluable patients within each cohort have at least 12 months of follow-up from the first PM01183 infusion. Patients with SCLC will be followed-up for at least 18 months after the last patient enrolled received the first PM01183 infusion.

3 OBJECTIVES AND ENDPOINTS

3.1 Primary Objective

- To assess the antitumor activity of lurbinectedin (PM01183) in terms of overall response rate (ORR), according to the RECIST v.1.1, in the following advanced solid tumors: SCLC, H&N, NETs, biliary tract carcinoma, endometrial carcinoma, BRCA 1/2-associated MBC, carcinoma of unknown primary site, GCTs, and EFTs.

3.2 Secondary Objectives

- To further characterize the antitumor activity of PM01183 in terms of duration of response (DR), clinical benefit [ORR or stable disease (SD) lasting over four months ($SD \geq 4$ months)], progression-free survival (PFS) by Investigator’s assessment (IA), and overall survival (OS) in each cohort of advanced solid tumors.
- To further investigate the antitumor activity of PM01183 in terms of ORR, DR, clinical benefit [ORR or $SD \geq 4$ months] and PFS by an Independent Review Committee (IRC) in the cohort of SCLC patients.

- To characterize the plasma pharmacokinetics (PK) of PM01183.
- To conduct an exploratory pharmacogenomic (PGx) and pharmacogenetic analysis.
- To evaluate the safety profile of PM01183 in this patient population.

3.3 Endpoints

The following are the endpoints defined in the protocol. See further detail in the efficacy section.

Primary Endpoint:

- Overall Response Rate (ORR) in each tumor type. ORR is defined as the percentage of patients with a confirmed response, either complete (CR) or partial (PR), according to the RECIST (v.1.1).

Secondary Endpoints:

Efficacy (all cohorts):

- Duration of Response (DR) by IA, defined as the time between the date when the response criteria (PR or CR, whichever one is first reached) are fulfilled to the first date when PD, recurrence or death is documented.
- Clinical Benefit by IA, defined as response or stable disease lasting over four months ($SD \geq 4$ months).
- Progression-free Survival (PFS) by IA, defined as the period of time from the date of first infusion to the date of PD, death (of any cause), or last tumor evaluation.
- PFS4/PFS6 by IA, defined as the Kaplan-Meier estimates of the probability of being free from progression and death after the first infusion at these time points (4 and 6 months).
- OS, defined as the period of time from the date of first infusion to the date of death or last contact in case of patients lost to follow-up or alive at the clinical cut-off established for the cohort.
- OS6/OS12, defined as the Kaplan-Meier estimates of the probability of being alive after the first infusion at these time points (6 and 12 months).

Efficacy (only in the SCLC cohort):

- ORR, Clinical Benefit, DR, PFS and PFS4/PFS6 by IRC. The same definitions detailed for IA but following IRC evaluation will be used.

Plasma Pharmacokinetics (PK) of PM01183

- Non-compartmental (NCA) PK parameters: area under the curve (AUC), maximum plasma concentration (C_{max}), clearance (CL) and half-life ($t_{1/2}$). Population PK parameters of the compartment model to be developed (initially based on Volumes and Clearance), and PK/PD correlation parameters, if applicable.

Pharmacogenetics:

- This analysis will be performed in those patients who signed the written informed consent (IC) for the pharmacogenetic sub-study. The presence or absence of known polymorphisms from a

single sample collected at any time during the study, but preferably just before treatment start in Cycle 1, will be assessed to explain the individual variability in the main PK parameters.

Pharmacogenomics (PGx):

- This exploratory analysis will be performed on prior available paraffin-embedded tumor tissue samples from consenting patients of any arm. This sub-study will include factors involved in DNA repair mechanisms (such as nucleotide excision repair, homologous recombination repair and mismatch repair) and other factors related to the mechanism of action of PM01183 or to the pathogenesis of the disease, and their expression will be analyzed at the mRNA or protein level by quantitative polymerase chain reaction (PCR) and immunohistochemistry (IHC), respectively; their polymorphisms and mutations might be also analyzed, if relevant. Their correlation with clinical response and outcome after treatment will be assessed.

Safety Profile:

- Clinical examinations.
- Clinical assessment of AEs and serious adverse events (SAEs).
- Changes in laboratory parameters (hematological and biochemical, including liver function tests).
- Reasons for treatment discontinuations.
- Reasons for dose reduction and treatment delays.

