10. Adverse events	As per NCI-CTCAE v.4.	Throughout the "on treatment" period.**

*A 3-day window will be allowed for laboratory procedures and ECG, a 1-week window for radiological tumor assessments (helical CT-scan or MRI) and LVEF assessments and a 1-day window for clinical assessments (ECOG PS, physical examination, vital signs, weight, BSA).

** "On treatment period" = from first PM01183 infusion to EOT [30 days after the day of the last PM01183 infusion, unless the patient starts a new antitumor therapy or dies (whichever occurs first), in which case the date of administration of this new therapy or the date of death will be considered the date of EOT].

AAGP, alpha-1 acid glycoprotein; AE, adverse event; ALT, alanine aminotransferase; AP, alkaline phosphatase;

	ASSESSMENT	TIME
--	------------	------

AST, aspartate aminotransferase; β -hCG, beta subunit of human chorionic gonadotropin; BSA, body surface area; CPK, creatine phosphokinase; CT, computed tomography; ECG, electrocardiogram; ECHO, echocardiography; ECOG, Eastern Cooperative Oncology Group; EOT, end of treatment; GGT, gamma-glutamyltransferase; INR, international normalized ratio; LDH, lactate dehydrogenase; LVEF, left ventricular ejection fraction; MRI, magnetic resonance imaging; MUGA, multiple-gated acquisition scan; NCI-CTCAE, National Cancer Institute Common Terminology Criteria for Adverse Events; PK, pharmacokinetic; PS, performance status; PT, pro-thrombin time; PTT, partial thromboplastin time; ULN, upper limit of normal; WBC, white blood cells.

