5.8 EVALUATIONS AT END OF TREATMENT

The *end-of-treatment visit* will be scheduled within 30 days (\pm 7 days) after the last PM01183 infusion, unless the patient starts a subsequent antitumor therapy, in which case the end-of-treatment visit should be performed immediately before the start of the new therapy (ideally the day before or the same day).

Patients, regardless of the reason for ending the treatment, will have to undergo at the end of treatment the following assessments:

- Complete physical examination.
- ECOG PS.
- Vital signs.
- Concomitant therapies.
- Laboratory tests (coagulation panel, hematology and biochemistry A and B).
- Pregnancy test, ECG or LVEF assessment (if clinically indicated).
- Radiological tumor assessment (the evaluation should be repeated at EOT visit, if not previously done, and if the reason for treatment discontinuation is other than PD).
- Adverse events.

These evaluations will only have to be repeated for those parameters for which no measurement is available within 10 days before the EOT visit, or for those parameters with values that were out of range in the last assessment (grade \geq 2 according to the NCI-CTCAE v.4).

Adverse events must be reported for 30 days after the last study treatment administration. All serious adverse events (SAEs) occurring within 30 days of the last study treatment administration or until the start of a new antitumor therapy, whichever occurs first, will be reported. Beyond this period of time, only those suspected to be treatment-related SAEs will be reported (Section [7.7.2](#)).

The Sponsor will evaluate all safety information that is spontaneously reported by an Investigator beyond the time frame specified in the protocol.

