6.3 STARTING DOSES AND SCHEDULE

Starting dose will be 3.2 mg/m². Dose will be capped at BSA of 2.0 m² (i.e., dose will not exceed 6.4 mg).

Patients will receive PM01183 i.v. as a one-hour infusion on Day 1 every three weeks (q3wk) (three weeks = one treatment cycle).

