7. STUDY EVALUATIONS

7.1 EFFICACY

The primary objective of this study is to assess the antitumor activity of PM01183 in terms of **overall response rate (ORR)**, primary endpoint, supported by the secondary endpoint duration of response (DR), both assessed by the IA.

ORR will be assessed using the RECIST v.1.1 (see [APPENDIX 4](#)) on a set of measurable lesions identified at baseline as target lesions or as non-target lesions (if any), and followed until disease progression (PD) by an appropriate method (e.g., helical CT-scan, MRI).

Radiological tumor assessment will be performed at baseline, and every two cycles from the onset of the study treatment until Cycle 6 or evidence of PD. After Cycle 6, tumor assessment will be performed every three cycles until evidence of PD. If an objective response is observed, according to the RECIST v1.1, it must be confirmed by the same method at least four weeks after the date of the first documentation of response.

ORR is defined as the percentage of evaluable patients with a confirmed response, either complete (CR) or partial response (PR), from the start of treatment to the date of progression or the start of a subsequent therapy or end of patient's follow-up, according to the RECIST (v. 1.1).

DR will be calculated from the date of first documentation of response to the date of first documented PD, recurrence or death due to any cause in the responder patients.

The date of response, the date of radiological or clinical PD, according to the investigator assessment and the independent assessment by IRC when applicable (i.e., SCLC cohort), and the date of death will be registered and documented, as appropriate.

A copy of CT-scans or MRIs can be requested by the Sponsor in selected cases.

In SCLC patients, anonymized copies of all the images obtained throughout the study must be submitted to the Sponsor. These copies of CT scans, MRIs and any other documented methods to evaluate tumor response or progression in the SCLC cohort should be available for external radiological review by an IRC. The IRC will determine the patient's best response and assign the date of first documentation of response and progression/censoring according to RECIST v.1.1.

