Progression-free survival (PFS) is defined as the time from the date of start of treatment to the date of documented progressive disease (PD) by RECIST v1.1 or death (regardless of the cause of death), whichever comes first. Patients who progress or die will be considered to have had an event of progression, except if this event occurs after the start of subsequent antitumor therapy, in which case the patient will be censored at the time of last disease assessment prior to or on the first day of the first subsequent antitumor therapy. If the patient is lost for the assessment of progression during the follow-up period, or has more than one missing follow-up between the date of last tumor assessment and the date of progression, death or further antitumor therapy, the PFS/DR will be censored at the date of last valid disease assessment before the missing evaluations.

The date of response, the date of radiological progression, according to the investigator assessment and the independent assessment by IRC when applicable (i.e., SCLC cohort), the date of clinical PD and the date of death will be registered and documented, as appropriate.

Overall survival (OS) is defined as the time from the date of start of treatment to the date of death or last contact. **One year (1y-OS)/6 months overall survival** is defined as the Kaplan-Meier estimate of the probability of patients being alive at 12/6 months after the date of start of treatment.

A sensitivity analysis for all cohorts but SCLC will be performed for ORR, Clinical Benefit Rate, PFS and OS in the “All Treated Patients population”. For the SCLC cohort, the sensitivity analysis will be carried out the “All Evaluable Patients”.

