6.2.2 Secondary Endpoints

Exact binomial estimates with 95% confidence intervals (CIs) will be performed in the SCLC cohort for the analysis of the ORR according to RECIST v1.1 by IRC.

Time-to-event endpoints (DR, PFS and OS) and their set time estimates (i.e. PFS4, PFS6 and OS 6/12) will be analyzed according to the Kaplan-Meier method.

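### Do PFS4 and PFS6 need a second estimate because the 4- and 6-month readings fall just before the week-18 and week-27 scans?

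*SAP*

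**What the plan says.** The endpoint definition in SAP 3.3 (and, in the same terms, Protocol 3.2) makes PFS4 and PFS6 Kaplan-Meier readings: they are "defined as the Kaplan-Meier estimates of the probability of being free from progression and death after the first infusion at these time points". SAP 6.1 runs PFS from the start of treatment to "the date of documented progressive disease (PD) by RECIST v1.1 or death", whichever comes first. SAP 6.2.2 adds that the time-to-event endpoints and "their set time estimates (i.e. PFS4, PFS6 and OS 6/12) will be analyzed according to the Kaplan-Meier method". No interval-censored analysis is planned.

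The scan calendar comes from the protocol. Section 6.3 sets "three weeks = one treatment cycle". Section 7.1 calls for imaging "every two cycles from the onset of the study treatment until Cycle 6 or evidence of PD". It continues: "After Cycle 6, tumor assessment will be performed every three cycles until evidence of PD". The footnote to Table 4 in section 5.7 allows "a 1-week window for radiological tumor assessments" without giving its direction. Scans outside this grid also occur: confirmatory scans in responders (5.7), two-monthly scans after stopping without progression (5.9), and an end-of-treatment scan, where "the evaluation should be repeated at EOT visit, if not previously done, and if the reason for treatment discontinuation is other than PD" (5.8).

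Neither document defines the length of a month, states an expected PFS, or sets a target for PFS4 or PFS6.

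**The concern.** A progression that begins between two scans is dated at the later one. If the time point sits just before a scan, almost a whole scan interval of progressions is still unrecorded when the curve is read. The 4-month reading then reflects mainly the week-12 scan, and the 6-month reading mainly the week-18 scan. The error runs in one direction: the reported proportion exceeds the proportion truly free of progression.

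The trial has a single arm, so no concurrent group shares the scan schedule. A reader who takes the words of SAP 3.3 at face value, or sets these figures beside a study scanned on another calendar, could credit the drug with an effect of timing. The one related analysis counts clinical progression as an event (SAP 8.11, Tables 11.3.3.34 and 11.3.3.35). It covers SCLC only and leaves the dating of radiological progression unchanged.

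**Working it through.** **Calendar.** Assume 30.4375 days per month.

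- Scans: 2, 4, 6 and 9 cycles × 21 days = days 42, 84, 126 and 189.
- 4 months: 4 × 30.4375 = 121.75, so 126 − 121.75 = 4.25 days before the week-18 scan.
- 6 months: 6 × 30.4375 = 182.6, so 189 − 182.6 = 6.4 days before the week-27 scan.
- Months of 28 to 31 days give days 112 to 124 and 168 to 186, still before both nominal scans.

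**Window.** If scans are uniform over ±7 days, week-18 scans run from day 119 to day 133, and (121.75 − 119)/14 = 20% fall by 4 months. For week 27 the share is (182.6 − 182)/14 = 4%. If scans are instead done in the week before the nominal day, 2.75/7 = 39% of week-18 scans precede the reading. The PFS4 gap therefore lies inside the scan window.

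**Size.** The documents give no PFS distribution, so this step is conditional. Take exponential PFS with median 3.5 months, S(t) = 2^(−t/3.5). This is one of the two second-line SCLC medians in Protocol 1.1; the other is 4.1. If every event is a progression dated at a nominal scan, Kaplan-Meier at 4 months equals S(day 84), and at 6 months S(day 126):

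- PFS4: 57.9% − 45.3% = 12.6 points.
- PFS6: 44.1% − 30.5% = 13.6 points.

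Simulation with the ±7-day window lowers these to 10.3 and 13.0. If a share d of first events are deaths (exact dates) and a share p of progressions are found promptly outside the scan grid, only the remainder is delayed. The excess is then (1 − d)(1 − p) times the windowed value. With d = 20%:

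| p | PFS4 excess | PFS6 excess |
|---|---|---|
| 0% | 0.8 × 10.3 = 8.2 | 0.8 × 13.0 = 10.4 |
| 30% | 0.56 × 10.3 = 5.8 | 0.56 × 13.0 = 7.3 |
| 50% | 0.4 × 10.3 = 4.1 | 0.4 × 13.0 = 5.2 |
| 70% | 0.24 × 10.3 = 2.5 | 0.24 × 13.0 = 3.1 |

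Simulations of 200,000 or more patients per scenario agree to within about 0.1 point. Over medians of 2.5 to 7 months and 0 to 30% deaths, the excess runs from 13.0 (PFS6, no deaths, none prompt) down to 1.5 (70% prompt, extra scans, some delayed cycles). With scans in the week before the nominal day, the PFS4 excess at d = 20% is 6.9 with none prompt and 3.5 with 50% prompt.

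**Against sampling error.** The simulated standard deviation of Kaplan-Meier PFS4 (median 3.5, 20% exact-dated events) is 4.9 points at n = 100 and 9.9 at n = 25. The 95% intervals are then about 2 × 1.96 × 4.9 = 19 and 2 × 1.96 × 9.9 = 39 points wide.

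**What an extra row would give.** In simulation a Turnbull estimate with linear interpolation brings the bias to about 1 point either way, with bootstrap coverage of 91.3 to 94.7%. But 4 and 6 months fall inside the scan gaps (84 to 126 and 126 to 189 days). There the nonparametric curve is not determined, so the value read depends on the interpolation rule or on a model.

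**Comparison with other studies.** Suppose a comparator has the same true PFS (median 3.5, 20% deaths, none prompt) and is scanned every 6 weeks. Its own Kaplan-Meier excess is 8.2 at 4 months and 2.4 at 6 months. Kaplan-Meier against Kaplan-Meier is then off by −0.1 at PFS4 and +8.0 at PFS6. Setting an unbiased figure beside that comparator would instead be off by about −8 at PFS4. Neither estimator is safer across the board.

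**The case for a change.** The best case for acting is that the effect has a known direction, nothing planned measures it, and the row is cheap because assessment dates are already collected (Listings 14.1.23 and 14.1.24). IRC review works from the same scans, so IA and IRC agreement cannot expose it. In SCLC the worst cases, 8 to 10 points, are about as large as the half-width of the interval. SAP 8.9 also says that date imputation for time-to-event variables should be conservative.

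Much of this stands: the calendar, the direction, and the absence of a planned measure. The rest does not carry a change. SAP 8.9 concerns incomplete dates, not scan dates that are fully known. The claim that the figure is too high holds only against latent progression, which neither document takes as its target. Nor is the timing hidden. Kaplan-Meier PFS plots are planned for every cohort (Figures 11.3.2.4 and 11.3.3.11.1 to 11.3.3.11.3), and clustered scan-dated progressions would show as steps near weeks 18 and 27, although the plots would not quantify the lift. The same grid also affects median PFS, PFS at 12 months and duration of response, so correcting two time points alone would be selective.

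**Conclusion.** The plan can stand as written. PFS4 and PFS6 are conventional, internally consistent estimates of freedom from documented progression and death, and their Kaplan-Meier form is fixed in the endpoint definition itself. Read as freedom from latent progression they are probably too high, by about 1.5 to 13 points. That range rests on exponential PFS, an assumed share of deaths and, above all, an assumed share of progressions found off schedule; the documents supply none of these. The 4-month part is the less firm, because its 4.25-day gap sits inside the scan window.

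Nothing in the trial's decisions moves with these figures, and ORR is unaffected. A second estimate would answer a different question, would need its own modelling choice, and would be informative mainly in SCLC (100 patients) and endometrial carcinoma (50). Statisticians may reasonably differ on whether to show it. An analyst can state the scan schedule and month length beside the tables as ordinary good reporting, with no amendment to the plan.
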